9.8 Study Assessment Visit Windows

A window of ± 5 days will pertain to visits to allow flexibility for patient scheduling (± 15 days for follow-ups beyond week 10).

10.0 EVALUATION DURING TREATMENT/INTERVENTION

The below time and events table reflects 6-week course of rucaparib and RT, including boost. Note that participants receiving a 6-week course of rucaparib and RT will continue rucaparib maintenance therapy at the same dose level for 4 weeks after RT completion.

Table 10A.

	Pre-Study (within 30 days of starting treatment)	Wk 1	Wk 2	Wk 3	Wk 4	Wk 5	Wk 6	Wk 7	Wk 8	Wk 9	Wk 10	Follow up _b
Rucaparib _a		X	X	X	X	X	X	X	X	X	X	
Radiation therapy		X	X	X	X	X	X					
Informed Consent	X											
Demographics	X											
Medical History	X											
Concomitant medications	X	X		X			X		X		X	
Physical Exam _b	X	X	X	X	X	X	X	X	X	X	X	X
Adverse Event Monitoring	X	X	X	X	X	X	X		X		X	X
Vital signs _c	X	X		X			X		X		X	X
Height	X											
Weight	X											

ECOG Performance Status	X										
CBC with differential and platelets	X	X		X			X		X		X
Metabolic panel ^d	X	X		X			X		X		X
12-lead ECG	X										
Pregnancy test ^e	X	X _k									
Tumor specimen procurement ^{f,g}	X										
Patient Outcomes Questionnaire - BCTOS ^{h,i}	X										X
Patient Cosmesis evaluation (RTOG) ^{h,i}	X										X
Physician Cosmesis evaluation (RTOG) ^{h,i}	X										X
Digital breast images ^j	X										X
Drug diary		X	X	X	X	X	X	X	X	X	

- Rucaparib will be administered concurrently with RT, commencing with fraction #1 and daily throughout RT
- Patients will be seen by either their medical or radiation oncologist with only one toxicity assessment per visit. Follow up every 6 months for 2 years. Follow-up windows will be +/- 15 days.
- Vital signs include: temperature, pulse rate, respiratory rate, blood pressure, pulse oximetry.
- Metabolic panel containing: sodium, potassium, chloride, bicarbonate, BUN, creatinine, glucose, total protein, albumin, bilirubin, alkaline phosphatase, AST, ALT, corrected calcium, magnesium.
- Pregnancy test to occur within 14 days prior to study treatment
- Tumor specimen taken at time of definitive surgery if available
- Blood draw for germline DNA for control whole exome sequencing.
- BCTOS and cosmesis evaluations at baseline and at year 1 and 2.
- BCTOS and cosmesis evaluations only for breast-conservation patients and mastectomy patients with reconstructions.
- Digital photographs at baseline and at year 2.

k. It is strongly encouraged that women of childbearing potential undergo monthly serum pregnancy testing while you are taking study drug and for 6 months afterward. These tests can be completed at a local location and the patient should share these results with MSK.

Table 10B

Evaluation	Definition
Medical History	Medical history will be obtained and documented. It will include all active conditions, and any condition diagnosed within the prior 10 years that are considered to be clinically significant by the Investigator.
Concomitant Medications	Medications will be recorded, if any, taken by the subject during the trial. Concomitant medication and supportive care guidelines are detailed in Section 4.3. All medications related to reportable SAEs and ECIs should be recorded as defined in Section 6.0.
Physical Exam	A complete physical exam will be performed during the screening period and documented. Clinically significant abnormal findings should be recorded as medical history.
Vital signs	Vital signs (temperature, blood pressure, respiration rate, and pulse oximetry) assessed at screening, wk 1, wk 3, wk 6, wk 8 and wk 10, as specified in Table 10A.
Laboratory Assessments	For documentation of any hematologic abnormalities meeting CTCAE v 4.03 adverse event criteria, CBC with differential and platelets and a comprehensive metabolic panel (sodium, potassium, chloride, bicarbonate, BUN, creatinine, glucose, total protein, albumin, bilirubin, alkaline phosphatase, AST, ALT, corrected calcium, magnesium) will be drawn at baseline, week 1, week 3, week 6, week 8, and week 10.
Adverse Event Monitoring	All adverse events will be assessed and documented at study visits described, regardless of whether the event is a dose limiting toxicity. Events will be graded according to CTCAE 4.03 and entered into the study database.
Tumor Specimen	Formalin-fixed paraffin embedded specimens from the diagnostic cores and the lumpectomy specimen will be collected if available.
Drug Diary	Patients will be given a drug diary to record compliance with administration of study drug rucaparib. Patients will be educated on use of the patient diary prior to receiving study drug. Drug diaries will be reviewed for completion at patient visits.

Follow-up Visits	Subjects who discontinue trial treatment will move into the follow-up phase and should be assessed every 6 months for 2 years by a medical oncologist or radiation oncologist,
Patient Reported Outcomes and Cosmesis	
Patients will report patient satisfaction using the Breast Cancer Treatment Outcome Scale (BCTOS) (Appendix B). This self-report instrument has been used in a number of studies for this purpose and has both reliability and validity²⁰
 
Patients will first complete this after informed consent, and then at multiple intervening assessment points up to 2-years of follow-up (see study calendar, Table 10A).
 
At the same time points, patients will also score cosmesis using the RTOG 4-point scale with supplemental questions (Appendix C).
 
The RTOG cosmetic evaluation will also be completed by the radiation oncologist after consent and prior to treatment. This will be done using the RTOG scale with supplemental questions, using criteria established in previous RTOG trials (Appendix D).

Digital Images	
Digital images of patients' breasts will be taken after consent and prior to initiation of treatment, as well as at 2 years (see Study Calendar, Table 10A). The images will be taken using the cameras available in radiation oncology simulation rooms. The initial images can be ideally be taken at the time of simulation. The images will be uploaded in the patients radiation oncology EMR, which is a secure, password protected EMR and where the patients routine set-up pictures are stored.
 
Two pictures will be taken at each time point, taking care to exclude the patient's face. The first image will be of the breast to be treated and at a 45 degree oblique angle with arms elevated overhead.
 
The second image should be at a straight angle and frontal view of both breasts taken in either a standing or seated position with the patient's hands on her hips, taking care to exclude her face. These pictures will be taken at baseline (prior to any treatment), and at 2 years.

BCTOS (Appendix B):

The Breast Cancer Treatment Outcome Scale (BCTOS) is a 22-item measure of perceived aesthetic (e.g., breast shape) and functional status (e.g., pain, mobility) after breast

conserving surgical treatment and radiotherapy (BCT)¹⁷. This self-report instrument has demonstrably high reliability and validity, and is commonly used in this setting, allowing for cross comparison between trials of BCT. These endpoints will be assessed at baseline prior to start of RT, and at year 1 and 2. This tool includes items that focus specifically on radiotherapy-relevant symptoms (e.g., reports of skin problems, tenderness in the breast, hardness in the breast due to enhanced fibrosis, and pain).

Patients are asked to rate the items with respect to the magnitude of differences between the treated and untreated breast areas on a 4-point scale (1 = None, 2 = Slight, 3 = Moderate, 4 = Large). The BCTOS is scored to form three subscales: functional status (7 items), cosmetic status (8 items), and breast specific pain (3 items). The remaining 4 items (i.e., arm heaviness, fit of sleeve, arm swelling, and breast swelling) are not scored, but are included in the instrument as exploratory items because of their potential clinical importance. Each subscale is scored by calculating the mean of the item responses and ranges from 1 to 4. In the initial BCTOS validation, internal consistency reliability was 0.91 for functional status, 0.89 for cosmetic status, and 0.81 for breast specific pain

RTOG cosmesis scales:

The RTOG has developed patient (Appendix C) and physician (Appendix D) reported cosmesis assessment tools. These tools are notable for their simplicity, and although their validity has not been published by RTOG, they have been used in two recently completed but not reported seminal trials of breast RT- RTOG 0413/NSABP B39 and RTOG 1005¹. The control arms from these data sets will serve as important controls for us to compare to, hence we will use them.

Digital photographs assessment:

The EORTC Breast Cosmetic Rating system is a digital photographic method that has been utilized in prior radiation studies and shown to be reliable and valid in detecting effects of radiation morbidity^{21,22}. This method compares the radiated breast with the contralateral untreated side and qualitatively evaluates: breast size, breast shape, position of the nipple, shape of the areola, appearance of the surgical scar, skin pigmentation changes, and a global cosmetic score based on all of the factors. Each parameter is scored independently; the global score is scored qualitatively to account for the other factors. Characteristics are graded on a four-point scale: 0, excellent or no difference; 1, good or small difference; 2, fair or moderate difference; and 3, poor or large difference. One non-treating physician and one nurse will score each set independently. Discrepancies will be resolved by consensus.

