1.0 PROTOCOL SUMMARY AND/OR SCHEMA

The primary objective of the study is to determine the maximum tolerated dose (MTD) of rucaparib in combination with breast and nodal radiotherapy (RT) in women with triple negative breast cancer (TNBC) with residual disease following neoadjuvant chemotherapy or high grade hormone receptor (HR) positive disease with high volume residual following neoadjuvant chemotherapy. Secondary objectives are to describe the toxicities and disease outcomes and to identify biomarkers of locoregional relapse following rucaparib plus RT.

[figure not shown]
This is an amended protocol in which we add additional negative dose escalation levels to allow probing of the MTD into lower doses of rucaparib. In the original design, we had one -1 dose level, but we have exceeded the observed DLT for the TITE-CRM threshold at this level (see Biostatistics, section 14). We now add 3 additional de-escalation (-2, -3, and -4 dose levels). It is not surprising that even low dose levels of a PARP inhibitor may have radiosensitizing effects; for this reason we add 3 additional de-escalations.

Eligibility criteria include stage I-III TNBC patients with residual invasive disease following neoadjuvant chemotherapy (NAC), as well as high grade HR positive disease with high volume residual (4 or more positive axillary nodes, or 5 cm or more of residual breast disease) after NAC. Tumor tissue will be collected at the time of surgery, if available, precluding the need for an extraneous biopsy.

Treatment will consist of rucaparib at one dose level (200 mg QD, 300 mg QD, 200 mg BID, 300 mg BID, 400 mg BID, 500 mg BID, 600 mg BID) throughout a 6-week course of RT and then 4 weeks of maintenance rucaparib, at the same dose level, following RT. RT dose will consist of 50 Gy in 2 Gy/fraction to the breast or post-mastectomy chest wall, with or without nodes plus a 10 Gy boost to the lumpectomy cavity or (optionally) to the mastectomy scar (total dose 60 Gy). Patients will be followed for evaluation of toxicity with weekly assessments during the 10-week study period. For post-mastectomy patients not treated with a boost (ie only 5 weeks of radiation), rucaparib will be continued for 4 weeks post-RT for a total of 9 weeks. Patient-reported outcomes will be assessed and subject drug diaries will be maintained. Patients will then be followed every 3-6 months for two years, as per standard follow-up care.

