4.2 Intervention

Treatment will consist of rucaparib at one dose level (200 mg QD, 300 mg QD, 200 mg BID, 300 mg BID, 400 mg BID, 500 mg BID or 600 mg BID) concurrently with a 6-week course of radiotherapy and 4 additional weeks of maintenance rucaparib at the same dose level.

Radiotherapy will consist of 50 Gy in 2 Gy per fraction to the breast or chest wall with or without regional nodes plus a 10 Gy boost to the lumpectomy cavity, to a total dose of 60 Gy. A 10 Gy boost to the post-mastectomy scar is allowed at the discretion of the treating physician.

Weekly assessments for DLTs will be performed throughout RT, and every other week during the maintenance rucaparib period.

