9.5 Definition of Dose-Limiting Toxicity

Dose-limiting toxicity (DLT) will be defined as toxicities probably or definitely related to the study drug observed during the 70 days that include 6 weeks of radiotherapy and 4 weeks of maintenance rucaparib therapy, as follows:

- Confluent moist desquamation, defined as the presence of a single, contiguous region of moist desquamation that exceeds 25 cm² in area
- Absolute Neutrophil Count <1,000/mm³, with or without fever
- Platelet count <50,000/mm³
- Hemoglobin <8.0 g/dl
- Any ≥ Grade 3 non-hematologic toxicity by the NCI CTCAE version 4.03, not including Grade 3 ALT/AST elevation provided bilirubin and alkaline phosphatase meet criteria in Section 11.2
- Any toxicity requiring a RT dose delay exceeding 5 business days

Toxicities meeting this definition and occurring during the observation period of 10 weeks (70 days) will influence the dose level assignment of the TITE-CRM algorithm if these toxicities are deemed probably or likely related to study therapy.

Sites should contact the coordinating center as soon as possible (within one business day) when a DLT occurs or seems imminent. Sites should call [name] [name], and send an email to [name] [name] and study coordinator.

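### Three of the six DLT criteria are blood counts, but no count is scheduled at three of the six weekly DLT assessments in RT, so count-based DLTs may be found late or missed

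*Combined protocol and SAP*

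**What the plan says.** Section 9.5 lists six DLT criteria for the 70-day observation period. Three are laboratory counts: "Absolute Neutrophil Count <1,000/mm³, with or without fever", "Platelet count <50,000/mm³" and "Hemoglobin <8.0 g/dl". A fourth, the non-hematologic criterion, has an exception for Grade 3 ALT/AST elevation that depends on bilirubin and alkaline phosphatase.

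On how often DLTs are assessed, Section 4.2 states: "Weekly assessments for DLTs will be performed throughout RT, and every other week during the maintenance rucaparib period". Section 1.0 goes further: "Patients will be followed for evaluation of toxicity with weekly assessments during the 10-week study period".

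On blood draws, Table 10B says the CBC and metabolic panel "will be drawn at baseline, week 1, week 3, week 6, week 8, and week 10". In Table 10A the row "CBC with differential and platelets" is marked at pre-study and at the same five treatment weeks. The adverse event row is marked at weeks 1 to 6, 8 and 10.

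Section 9.8 sets the timing tolerance: "A window of ± 5 days will pertain to visits to allow flexibility for patient scheduling".

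Section 14.0 weights each DLT-free patient by the time followed within the observation period. Table 11B attaches a recorded DLT and a treatment action to the three count thresholds.

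**The concern.** A neutrophil, platelet or hemoglobin DLT without symptoms can be seen only if blood is drawn. Of the six weekly DLT assessments in RT, those at weeks 2, 4 and 5 have adverse event monitoring but no scheduled CBC or metabolic panel. Half of the DLT list then has no scheduled measurement. Nothing elsewhere in the protocol adds a CBC: the extra weekly tests in Section 11.2 are liver tests, and they start only after a Grade 3 or 4 ALT/AST elevation has been found. The longest interval, week 3 to week 6, lies within combined rucaparib and RT, and Table 11A lists anemia, neutropenia and thrombocytopenia among the drug's principal side effects.

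Two things are at stake. The first is the primary endpoint. While a count-based DLT is unseen, the patient adds DLT-free weight to the model that assigns the next patient's dose. If the count recovers before the next draw, she also enters the final estimate as a non-DLT. The second is the patient: neither the Table 11B action nor the one-business-day notice in Section 9.5 can act on a count that was not taken.

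**Working it through.** **Inputs from the documents.** Six DLT criteria, three of them counts (9.5). DLT assessments at weeks 1 to 6, then every other week (4.2; adverse event row of Table 10A at weeks 1–6, 8, 10). CBC at weeks 1, 3, 6, 8, 10 (Tables 10A, 10B). Window ±5 days (9.8). Observation period 70 days (9.5). Simulated accrual 4 per 70 days (14.0). The plan states no detection probability, so there is no figure of its own to reproduce.

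**Step 1: intervals between draws.**
- Weeks 1→3→6→8→10 give 14, 21, 14 and 14 days. The longest is 21 days.
- With week 3 taken 5 days early and week 6 taken 5 days late: 21 + 5 + 5 = 31 days.
- If draws matched the Section 4.2 assessments, the longest interval in RT would be 7 days, or 7 + 10 = 17 days at the window extremes.

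**Step 2: effect of late detection on the TITE-CRM.** Taking weight as proportional to follow-up, an unseen DLT counts as DLT-free for up to 21/70 = 30% of the window, or 31/70 = 44% with the window. At the simulated accrual, 21 × 4/70 = 1.2 new patients are expected in a 21-day interval.

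**Step 3: chance that an episode contains no scheduled draw.** The documents give no cytopenia durations, so the length L is an assumption. Take draws at the end of each named week (days 7, 21, 42, 56, 70), and onset uniform from day 7 to day 70 − L. Then the missed share = Σ max(gap − L, 0) / (63 − L).

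| L (days) | Schedule as written (gaps 14, 21, 14, 14) | Draws at stated assessments (gaps 7 ×5, 14, 14) |
|---|---|---|
| 7 | (7+14+7+7)/56 = 62.5% | (7+7)/56 = 25% |
| 10 | (4+11+4+4)/53 = 43% | (4+4)/53 = 15% |
| 14 | 7/49 = 14% | 0% |
| 21 | 0% | 0% |

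Within the longest interval alone the missed share is 1 − L/21: 67%, 52%, 33% and 0%. If that interval stretches to 31 days, a 10-day episode is missed 1 − 10/31 = 68% of the time, and a 21-day episode 1 − 21/31 = 32%. The 0% at 21 days therefore requires visits on time.

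**Step 4: sensitivity to the timing assumption.** With onset uniform over all 70 days, 7-day episodes are missed 35/70 = 50% of the time (end-of-week draws) to 42/70 = 60% (start-of-week draws). With matched draws the figures are 14/70 = 20% to 21/70 = 30%. For 14-day episodes they are 7/70 = 10% to 14/70 = 20%, against 0% to 7/70 = 10%.

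**Step 5: from missed episodes to the DLT rate.** For a true rate of 30%, recorded rate = 0.30 × (1 − h × m), where h is the share of DLT patients whose only DLT is a count and m is the share of those missed. The documents give neither h nor m. Since both are at least zero, the bias is downward or zero, and that is as far as the arithmetic goes.

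**The case against.** Section 4.2 promises weekly assessments, not weekly draws, and the adverse event row of Table 10A matches it week for week. CBC frequency can be seen as a separate design choice. Unscheduled counts are not ruled out, and supportive care for cytopenias follows institutional guidelines. A count still below threshold at the next draw is recorded as a full DLT, only later. Rucaparib is taken continuously without dose modification, and the documents give no reason to expect short cytopenias that resolve while the drug continues.

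Most of this stands as a limit on size. A reader might infer that the DLT rate *is* understated. That is not shown: a DLT is lost only if the count recovers between draws, begins after the last draw, or is first found after day 70 (possible when the week 10 visit uses its +5 days). A reader might also infer a definite rise in the chance of selecting too high an MTD. That would need the DLT counts among the seven treated patients, and Section 14.0 gives only their allocation (two at level 0, five at level −1) and the statement that level −1 exceeded 30%. It would also need model settings that the plan does not fully state. No percentage for the MTD is supportable.

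What does not stand is that the two schedules are compatible as written. An assessment of a count threshold without a count covers at most its clinical signs, and the possibility of an unscheduled count is not a plan to take one.

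**Conclusion.** The mismatch is established from the text: the laboratory DLT criteria have no scheduled measurement at three of the six weekly RT assessments. Detection up to 21 days late (31 at the window extremes) follows by arithmetic from the calendar alone, if no unscheduled count is taken. Late detection affects dose assignments made in the interval; a missed episode also affects the final estimate. The recorded DLT rate may therefore be too low, and dose assignments may rest on incomplete data.

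The size is unknown. The missed shares in the table are illustrations that rest on assumed durations and uniform onset. If all count-based episodes last 21 days or more, visits are on time and a draw follows, nothing is missed and only the delay remains. The point deserves correction because it touches the primary endpoint and the protocol's own safety action, not because a particular bias has been demonstrated.

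**What to change.** Reconcile Sections 4.2, 9.5, 9.8 and Tables 10A/10B so that the laboratory DLT criteria, including the values needed for the ALT/AST exception, are measured at the DLT assessments the plan states. Settle at the same time whether assessments in maintenance are weekly (Section 1.0) or every other week (Section 4.2). The visit window should fit the chosen frequency: ±5 days around visits 7 days apart makes neighboring windows overlap by 5 + 5 − 7 = 3 days.

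Under the Section 4.2 frequency the cost is an amendment and up to three more routine blood draws per patient (weeks 2, 4 and 5), at visits already in Table 10A.

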10.1 Tumor Specimen Collection Guidelines

MSK is equipped with the necessary laboratory infrastructure (i.e. the [name] Lab) to conduct the exploratory studies. Patients will be consented for research retrieval, if available, of their initial diagnostic core biopsy specimens and their lumpectomy/mastectomy specimens. This consent should preferably happen in parallel to this study and on protocol 12-245. Patients not consenting to 12-245 can participate in the correlative research of this study through an optional consent clause in the informed consent. Specimens will be collected and transported to the Integrated Genomics Operations core at MSKCC. The specimens will be evaluated by H&E for adequacy and to plan for microdissection if it is needed. The core, led by [name], is experienced in handling FFPE material and extracting DNA and RNA from

such specimens. However, the results of our assays (determining HR-proficient vs HR-deficient) are not necessary for patients to receive the study treatment and will only be shared with the study statistician and primary investigator. Patients who are unable to obtain a definitive HRR status will not be excluded from analysis of the primary endpoint of the study, but may not be counted towards the secondary and exploratory objectives of the study.

For patients not consenting to 12-245, but opting into this study's specimen collection will have a baseline blood draw for germline exome sequencing as part of the pair with tumor exome sequencing.

